Brief Summary	This is a pilot study implemented physical activity assessment, promotion and monitoring in patients. Patients will be assessed by the physical activity vital sign (PAVS) during check-in for their appointment. During their visit with the cardiologist, a clinical decision support tool will alert the cardiologist to patients achieving low (<50% of recommended) physical activity. The cardiologist may refer the patient to cardiac rehabilitation if appropriate and/or counsel them to increase their physical activity levels. The patients may opt to enroll in the monitoring phase of the study. They will be given a Fitbit pedometer and their Fitbit account can sync to their MyChart account. After that sync, the patients step counts will be available for their cardiologists to review as needed.
Phase	Clinical study Phase 1
Objectives	
There are two objectives for this study.
 
Objective 1: Test the preliminary clinical efficacy of a PA promotion intervention on patients' cardiovascular risk profile (PA, cardiorespiratory fitness, BMI, waist circumference, blood pressure, lipids and Framingham Heart Study Risk Score).
 
Objective 2: Evaluate the implementation feasibility of the PA promotion intervention. The Practical, Robust Implementation and Sustainability Model (PRISM) will be used to guide the implementation, and evaluate the intervention's reach, efficacy, adoption, implementation and maintenance for both HCPs and patients, in addition to qualitative feedback on acceptability.

Methodology	This study is a pilot feasibility study implementing physical activity assessment, promotion and monitoring in a cardiology clinical setting.
Endpoint	The primary endpoints include: physical activity levels (step-counts), cardiorespiratory fitness, BMI, waist circumference, blood pressure, lipids and Framingham Heart Study Risk Score For our secondary endpoints we will conduct a process evaluation we will evaluate the intervention's reach, efficacy, adoption, implementation and maintenance using The Practical, Robust Implementation and Sustainability Model (PRISM).
Study Duration	A study duration of three years will include development of the clinical decision support tool, training clinic staff on intervention, recruitment, and data collection and analysis.
Participant Duration	Each participant will be in the study for 3 months. Baseline data collection is at Time 1; followed wearing the Fitbit for 3 months; and follow-up data collection at Time 2 (3 months).

CONFIDENTIAL

This material is the property of the NYU School of Medicine and Langone Medical Center. Do not disclose or use except as authorized in writing by the study sponsor

Interventional Template Version: 11 JAN 2019

Population	We will recruit 59 males and females age > 18 being seen in the NYU Langone Center for Prevention of Cardiovascular Disease (4F). Participants have cardiovascular disease or cardiovascular disease risk factors.
Study Site	NYU Langone Center for Prevention of Cardiovascular Disease (4F)
Number of participants	59 participants in one site
Description of Study Agent/Procedure	The intervention consists of physical activity assessment promotion and remote home step-count monitoring in a clinical cardiology center.
Reference Therapy	This is a one-group study. There is no comparison group.
Key Procedures	Key procedures include assessment of physical activity; counseling by the cardiologist if physical activity levels are <50% of recommended; remote home monitoring via Fitbit sync to MyChart.
Statistical Analysis	Paired t-tests will be used to assess changes in average PA from week 2 to three-month follow-up using PAVS and Fitbit Zip data. Paired t-tests will be used to assess changes in readiness to change number, the 6MWT, BMI, waist circumference, systolic and diastolic BP, lipids, and Framingham Heart Study Risk Score. To assess meaningful improvement in CRF, we will report the percent of participants who achieve a clinically important difference of 25 meters in the 6MWT. Bivariate analyses will compare all CVD risk factors, as well as other potential confounders (e.g. age, sex, race/ethnicity, depressive symptoms, comorbidities), between those who achieve PA recommendations and those who do not. Preliminary effect sizes of change in PA (step counts) will be generated following the Physical Activity Change Detection (PACD) approach. Aim 2 is to conduct a process evaluation of the intervention. Implementation data will be evaluated using the PRISM framework.

CONFIDENTIAL

This material is the property of the NYU School of Medicine and Langone Medical Center. Do not disclose or use except as authorized in writing by the study sponsor
Interventional Template Version: 11 January 2019

Flow diagram Single Group

Prior to enrollment: Present protocol to CTSI Patient Advisory Council for Research to solicit feedback on how to appeal to participants and improve engagement. Review protocol with participating cardiologists and medical assistants. Informatics team to develop clinical decision support tool in Epic.

Implement the collection of Physical Activity Vital Sign for all patients at appointment check-in via check-in kiosk. If patients report < 50% of recommended physical activity → alert to provider to refer to cardiac rehabilitation or counsel patients on improving physical activity levels. Cardiologists will describe remote monitoring phase of study and refer to PI or RA if interested. The PI or RA will describe the 3 months of patient remote home monitoring of physical activity using a Fitbit.

Total N=59 (single group): Obtain informed consent. Screen potential subjects by inclusion and exclusion criteria.

Time 1. Perform baseline assessments: physical activity vital sign, cardiorespiratory fitness (6-minute walk test), body mass index, waist circumference, blood pressure, lipids, Framingham Heart Study Risk Score, depressive symptoms (PROMIS), and quality of life (SF-36).

3 Months of Remote Home Monitoring of Physical Activity with Fitbit Step-counts syncing to MyChart in Epic.

Time 2. (3-months) Perform Follow-up assessments: physical activity vital sign, cardiorespiratory fitness (6-minute walk test), body mass index, waist circumference, blood pressure, lipids, Framingham Heart Study Risk Score, depressive symptoms (PROMIS), and quality of life (SF-36).

CONFIDENTIAL

This material is the property of the NYU School of Medicine and Langone Medical Center. Do not disclose or use except as authorized in writing by the study sponsor
Interventional Template Version: 11 January 2019

1 Key Roles

PI: [name], RN, FNP-BC,
Assistant Professor
NYU Rory Meyers College of Nursing.
[name]
[name]
[contact]
[contact]

Mentor for K23 Mentored Patient-Oriented Research Career Development Award

Co-I [name]
NYU Langone Health
[name]
[name]

NIH Point of Contact: NINR Program Director: [name]
National Institute of Nursing Research National Institutes of Health
[name]
[name]
[contact]
[contact]

2 Introduction, Background Information and Scientific Rationale

2.1 Background Information and Relevant Literature and Rationale

Physical inactivity is the fourth leading cause of death worldwide.¹ Despite the numerous benefits of routine physical activity (PA) (e.g., lower risk for heart disease, stroke, type 2 diabetes, and depression), only half of U.S. adults achieve the recommended levels of PA:² a minimum of 150 minutes/week of moderate-to-vigorous PA.³ Meeting PA guidelines could result in significant improvements in body fat, body mass index (BMI), blood glucose, and cardiorespiratory fitness.⁴ Improving these risk factors would lower the risk of cardiovascular disease (CVD) and stroke, the two leading causes of death in the U.S.⁵ The American Heart Association (AHA) and American College of Cardiology have recommended that healthcare providers (HCPs) counsel patients on adopting PA guidelines.⁶ While PA counseling trends are improving, little has been done in terms of routinely assessing PA in a standardized way.⁷ The first step in promoting PA is to assess patients' current habits.⁸ A 2018 AHA scientific statement on assessing and promoting PA in healthcare settings suggested use of the electronic health record (EHR) for self-report and activity trackers (e.g. Fitbit) for monitoring.⁹

The purpose of this feasibility study based on the Chronic Care Model¹⁰ is to address the low levels of PA in adults by testing a PA promotion intervention based on an EHR clinical decision support tool. This tool will facilitate HCPs in assessing and promoting patients' PA, and in turn patients will be involved in negotiating ways of increasing PA, which may improve their CVD risk profile. Clinical decision support tools have been used to screen for CVD risk and can play an important role in improving patient outcomes, particularly when the patient is involved.¹¹ In

CONFIDENTIAL

This material is the property of the NYU School of Medicine and Langone Medical Center. Do not disclose or use except as authorized in writing by the study sponsor
Interventional Template Version: 11 January 2019

response to the major health problem of physical inactivity, the 3-question physical activity vital sign (PAVS) was developed to assess PA duration and intensity.^{12,13}

According to the AHA physical inactivity is a major modifiable risk factor for CVD.¹⁴ Despite the strong evidence regarding the hazards of physical inactivity half of U.S. adults do not achieve the recommended levels of PA.² Moving individuals out of the lowest category of cardiorespiratory fitness results in the greatest reductions in all-cause mortality.³⁹ and can be achieved with increased PA.⁴ HCPs are in a position to influence this process by routinely counseling patients on this important CVD risk factor.

The U.S. 2018 PA Guidelines for Americans recommends 150 minutes/week of moderate intensity PA or 75 minutes/week of vigorous intensity PA, or an equivalent combination of both, with vigorous activity weighted twice that of moderate.³ Improving rates of HCP counseling on PA is one of the objectives of Healthy People 2020.¹⁵ The U.S. Preventive Services Task Force recommends referring adults with CVD risk factors seen in primary care to behavioral counseling interventions to promote PA for CVD prevention.¹⁶ HCPs can be instrumental sources of health guidance for their patients, but they do not routinely counsel patients on PA.^{15,17} PA counseling (face-to-face or by phone) offered on multiple occasions in primary care settings resulted in improved PA levels at 12 months in previously sedentary adults.¹⁸ Primary care behavioral counseling for CVD prevention was also associated with a 35-minute/week (95% CI: 22-47) improvement in PA levels.¹⁹ While the use of brief one-time counseling has not been shown to be enough to effect long-term change, routine office-based screening and advice coupled with ongoing support has been effective in improving PA.¹⁷ The AHA recommends the use of goal setting, self-monitoring, follow-up, and feedback when promoting PA.²⁰ In adults with CVD, wearing an activity tracker coupled with PA advice resulted in greater improvements in cardiorespiratory fitness (CRF) as compared to those not wearing an activity tracker.²¹ This proposal will address the gap in routine PA counseling with an intervention that standardizes the assessment, promotion and monitoring of PA in the clinical setting through utilization of the EHR.

The PAVS is a valid clinical tool to assess PA²² which can be the basis for PA promotion and counseling. Several large healthcare systems have implemented the PAVS for assessment of PA.⁷ Data from almost 20 hospitals indicate the PAVS has strong face and discriminant validity (between groups of patients with differing activity levels).²³ However, despite strong endorsement from the AHA,⁶ many HCPs continue to describe barriers to PA counseling, including lack of time, required counseling skills, reimbursement and routine screening of PA.²⁴ This proposed intervention, embedded in the EHR, expands upon the current use of the PAVS and may help to overcome the existing barriers to addressing PA. In a systematic review of behavior change techniques used in eHealth PA interventions in adults with CVD, providing information on health consequences, goal-setting and self-monitoring were the three most common behavior change techniques used.²⁵ Our intervention will educate the patient on PA recommendations, help them set goals, and employ a self-monitoring tool that has the added benefit of PA data syncing to the EHR.

2.2 Potential Risks & Benefits

2.2.1 Known Potential Risks

Potential risks associated with this research are fatigue from data collection, inconvenience caused by the need to schedule visits, and loss of confidentiality. There are also inherent risks to participating in physical activity. This will be minimized with the appropriate clinical judgement of the physician in the physical activity promotion process. There is a slight risk of loss of confidentiality in the data collection from the electronic health record, but this will be minimized

CONFIDENTIAL

This material is the property of the NYU School of Medicine and Langone Medical Center. Do not disclose or use except as authorized in writing by the study sponsor
Interventional Template Version: 11 January 2019

by the collection of de-identified data only. There are some risks during the fingerstick blood collection of lipids and glucose. With respect to fingerstick blood collection in general (requiring a small sample size of 40 μ L of blood), some participants may experience temporary discomfort. Some may bruise. Extremely rare risks associated with a fingerstick are bleeding, feeling lightheaded, hematoma, or infection. This risk will be minimized by following established hospital protocols for fingerstick blood collection.

2.2.2 Known Potential Benefits

There may not be direct benefit to patient subjects of this study. However, subjects may increase their physical activity levels enough to reduce their cardiovascular risk by reductions in weight, blood pressure or hemoglobin A1c or improvements in lipids. Subjects may gain of sense of contribution to the process of improving physical activity assessment and promotion.

3 Objectives and Purpose

The purpose of this feasibility study is to implement a physical activity intervention in a preventive cardiology clinic to assist HCPs in assessing, promoting and monitoring their patients' PA.

3.1 Primary Objective

Aim 1: Test the preliminary clinical efficacy of a PA promotion intervention on patients' cardiovascular risk profile (PA, cardiorespiratory fitness, BMI, waist circumference, blood pressure, lipids and Framingham Heart Study Risk Score).

3.2 Secondary Objectives (if applicable)

Aim 2: Evaluate the implementation feasibility of the PA promotion intervention. The Practical, Robust Implementation and Sustainability Model (PRISM)²⁶ will be used to guide the implementation, and evaluate the intervention's reach, efficacy, adoption, implementation and maintenance for both HCPs and patients, in addition to qualitative feedback on acceptability.

4 Study Design and Endpoints

4.1 Description of Study Design

This is a one-group, pre-post, single-center phase 1 clinical trial feasibility study based on the Chronic Care Model.¹⁰ This study has two phases.

Phase 1: The PI will train the medical assistants on the collection of the PAVS (in case the patient had not entered the kiosk data). The PI will meet the CTSI Patient Advisory Council for feedback on how to appeal to participants and improve engagement. The PI will review the plan and the American College of Sports Medicine exercise screening guidelines with the cardiologists and elicit final questions or feedback.²⁷

Phase 2: Each patient in the Center is seen by the medical assistant for the assessment of their vital signs and confirmation of the PAVS completion in the check-in kiosk. During the patient's visit with the cardiologist, an EHR decision support tool will be presented as an alert to the cardiologist for patients who are not achieving at least **50%** of recommended PA levels. This threshold was chosen for two reasons. A higher threshold (e.g. < 90%) would create many more alerts for the cardiologist and possibly lead to 'alert fatigue'. Second, our focus will be on the least active patients. The cardiologist will choose and acknowledge the PA promotion recommendations they discussed with the patient: #1) patients with a diagnosis appropriate for cardiac rehabilitation²⁸ will be given a suggested verbal and/or electronic referral to cardiac

CONFIDENTIAL

rehabilitation services; and/or #2) patients who are not eligible for a cardiac rehabilitation referral (or do not want to attend) will be given a verbal recommendation to start engaging in PA, or increase intensity and/or duration of PA with an agreed upon goal for the next 3 months. Patients who should not increase PA due to certain medical diagnoses (e.g. aortic stenosis, unstable angina) will be excluded. The cardiologist will inform these patients about the remote PA monitoring.

Upon contact, the PI will describe the study, and if patients agree to participate, obtain consent, enroll the participant and collect baseline data. The PI will give participant a Fitbit Zip, set up an account with a study ID and ask them to wear the Fitbit Zip during all waking hours. NYU Langone has implemented integration of Fitbit Zip data into the EHR which requires the patient to sync their Fitbit account to the patient portal (MyChart) once and step counts will then sync to EHR and can populate the cardiologists' note.

4.2 Study Endpoints

4.2.1 Primary Study Endpoints

For this feasibility study, we will implement the intervention (PA assessment using the PAVS; counseling by the cardiologists; and PA monitoring of patients wearing a Fitbit) for 12 months. Patient subjects who enroll in the PA monitoring will wear the Fitbit for 3 months. Primary endpoints include: patients' cardiovascular risk profile (PA, cardiorespiratory fitness, BMI, waist circumference, blood pressure, lipids and Framingham Heart Study Risk Score).

4.2.2 Secondary Study Endpoints

We will evaluate the implementation feasibility of the PA promotion intervention. The Practical, Robust Implementation and Sustainability Model (PRISM)²⁶ will be used to guide the implementation, and evaluate the intervention's reach, efficacy, adoption, implementation and maintenance for both HCPs and patients, in addition to qualitative feedback on acceptability.

5 Study Enrollment and Withdrawal

Cardiologists from Preventive Cardiology that have agreed to participate in this pilot study will have the study described and will sign an informed consent. Patient participants are those patients being treated in Preventive Cardiology. Their cardiologist can inform them of the study and given them the PI's contact information or introduce them to the PI or RA if they are present in the clinic. All patients who achieve < 50% of recommended PA and do not meet any of the exclusion criteria will have the study described to them. The PI or RA will confirm inclusion and exclusion criteria.

5.1 Inclusion Criteria

In order to be eligible to participate in this study, an individual must meet all of the following criteria:

Adult patients in the Center who are age 18 and above will be assessed with the PAVS as part of routine care. To enroll in the home monitoring of PA:

1. Patients must achieve < 50% of PA recommendations according to PAVS screening questions
2. Have a cellular phone with data plan or a computer to sync Fitbit data
3. Speak English or Spanish
4. Be willing to wear a Fitbit Zip for 3 months

CONFIDENTIAL

This material is the property of the NYU School of Medicine and Langone Medical Center. Do not disclose or use except as authorized in writing by the study sponsor
Interventional Template Version: 11 January 2019

5.2 Exclusion Criteria

An individual who meets any of the following criteria will be excluded from participation in this study:

1. Adults with a physical disability or medical diagnosis limiting their ability to exercise (e.g. wheelchair bound, aortic stenosis, unstable angina)
2. Planned surgery within three months
3. Those with decisional incapacity therefore unable to comply with study requirements (i.e. related to cognitive deficits or psychiatric diagnosis)
4. Pregnant or breastfeeding women.

5.3 Vulnerable Subjects

No vulnerable subjects are included in this study.

5.4 Strategies for Recruitment and Retention

Appropriate patients will be invited to participate by the cardiologist during the visit. They will be given a study information flyer and contact information of the PI, who will screen for inclusion/exclusion criteria. The informatics team at NYU Langone may also provide a list of patients on a monthly basis who achieve < 50% of recommended PA. This will facilitate recruitment in the event of virtual visits when the patient fills out the PAVS via MyChart.

The PI will contact the individual cardiologist by email to inform them of the intent to recruit their patient into the remote monitoring study. If the cardiologist has any objections, they can inform the PI. The 'Friendly' Letter to the Provider is attached. If met, the PI will enroll them in the study. If the PI is not immediately present in the Center, the interested patient will be given the PI contact information. The PI will also access the expertise of the NYU School of Medicine CTSI Recruitment and Retention Unit as needed for both recruitment and retention. Description of the study and consent for participation will take place in one of the offices in the Preventive Cardiology Center. The PI may also describe the study over the phone to patients who call after being referred by their cardiologist.

Retention strategy: While subjects are wearing the Fitbit they will be contacted the first week to check in and see if they have any questions. They will be contacted as needed over the 3 months if the PI or RA notice they are not wearing the Fitbit daily to troubleshoot ideas to improve their Fitbit wear time.

Our target sample size is 59 subjects. Our target is to enroll 2-3 subjects per week. When the PI or RA is not present in the clinic, a study flyer will be left with the cardiologists and staff.

5.5 Participation

Baseline data collection will take place on the day of consent. Each subject will be asked to wear a Fitbit pedometer for 3 months. Follow-up data collection will take place as close to the 3-month date as possible.

5.6 Total Number of Participants and Sites

This is a single site study conducted at the Preventive Cardiology Center (4F). All 59 subjects will be enrolled at this site.

Recruitment will end when approximately 59 subjects are enrolled. It is expected that approximately 59 participants will be enrolled in order to produce 47 evaluable subjects. We have anticipated approximately 20% attrition.

CONFIDENTIAL

This material is the property of the NYU School of Medicine and Langone Medical Center. Do not disclose or use except as authorized in writing by the study sponsor
Interventional Template Version: 11 January 2019

5.7 Participant Withdrawal or Termination

5.7.1 Reasons for Withdrawal or Termination

Participants are free to withdraw from participation in the study at any time upon request. An investigator may terminate participation in the study if:

- Any clinical adverse event (AE), laboratory abnormality, or other medical condition or situation occurs such that continued participation in the study would not be in the best interest of the participant
- The participant meets an exclusion criterion (either newly developed or not previously recognized) that precludes further study participation

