6.1.5 Final Study Visit

Final Study Visit (Visit 2; 3 months after baseline visit +/- 2 weeks)

- Record adverse events as reported by participant or observed by investigator.
- Collect follow-up data (surveys, fingerstick lipids, six-minute walk test, waist circumference, body mass index)

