6.1.6 Withdrawal/Early Termination Visit

If the patient subject terminates the study early and is willing to participate, the PI will collect follow-up data if the patient subject has completed at least 2.5 months of follow-up.

7 Assessment of Safety

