9.1 Statistical and Analytical Plans (SAP)

Aim 1. Analysis will be performed using SAS 9.4. Surveys will be administered using the Research Electronic Data Capture (REDCap) system,⁴² a secure web-based tool licensed and supported by NYU. Standard descriptive statistics will be used to describe baseline sociodemographic and clinical characteristics. Mean scores and standard deviations as well as Cronbach's α will be calculated on questionnaires to confirm reliability of study instruments in our sample. Week 2 of the Fitbit Zip PA data will be used as baseline to assure the participant is accustomed to the device and to minimize the effect of reactivity, which can last approximately one week.⁴³ To calculate total minutes/week of PA from PAVS, the following standard calculation will be used:⁴⁴ light activity will be multiplied by 0 (light activity is not included in PA recommendations but is collected to acknowledge all attempts at PA and encourage increased intensity); moderate activity is multiplied by 1; vigorous activity is multiplied by 2 (one minute of vigorous activity being equal to two minutes of moderate activity). Paired t-tests will be used to assess changes in average PA from week 2 to three-month follow-up using PAVS and Fitbit Zip data. Using Fitabase software which allows for high resolution data, we will compare minutes of PA in three levels of intensity (light, moderate, and vigorous) as well as minutes spent in sedentary behavior. We will report the percentage of weeks each participant achieves the recommended levels of PA during the monitoring period and will assess weekly PA trends. We will compare improvements in PA by levels of protocol adoption by the HCP (e.g. 100% vs. 50% adoption). At 3 months we will compare mean minutes of moderate-to-vigorous PA between those who report achieving recommended levels of PA by the PAVS to those who do not. Paired t-tests will be used to assess changes in readiness to change number, the 6MWT, BMI, waist circumference, systolic and diastolic BP, lipids, and Framingham Heart Study Risk Score. To assess meaningful improvement in CRF, we will report the percent of participants who achieve a clinically important difference of 25 meters in the 6MWT.⁴⁵ Bivariate analyses will compare all CVD risk factors, as well as other potential confounders (e.g. age, sex, race/ethnicity, depressive symptoms, quality of life, comorbidities), between those who achieve PA recommendations and those who do not.

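### Section 6.1.6 seeks outcomes after early termination only from 2.5 months, so willing participants terminated earlier have no planned 3-month assessment and fall out of the paired tests

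*Combined protocol and SAP*

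**What the plan says.** Section 5.7.1 gives two grounds on which an investigator may end participation. The first is an adverse event or similar: "laboratory abnormality, or other medical condition or situation occurs such that continued participation in the study would not be in the best interest". The second is "The participant meets an exclusion criterion (either newly developed or not previously recognized) that precludes further study participation". Section 5.2 opens its list of exclusions with "Adults with a physical disability or medical diagnosis limiting their ability to exercise"; the others are planned surgery within three months, decisional incapacity, and pregnancy or breastfeeding.

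For someone who leaves early and is willing, section 6.1.6 states that "the PI will collect follow-up data if the patient subject has completed at least 2.5 months of follow-up". The ordinary visit is defined in section 6.1.5 as "3 months after baseline visit +/- 2 weeks". Section 5.7.2 adds that people who withdraw stay under their cardiologist's usual care, that the reason and any adverse events are sought, and that only those who never complete baseline collection are replaced.

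On analysis, section 9.1 says "Paired t-tests will be used to assess changes in readiness to change number, the 6MWT, BMI, waist circumference", and continues with blood pressure, lipids and the Framingham score. The same test compares PAVS and Fitbit activity at 3 months with week 2. Section 9.2 says the pilot will give effect sizes for all patient participants. No section describes how a missing 3-month value is handled. Sections 5.6 and 9.3 expect 20% attrition, from 59 enrolled to 47 evaluable.

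**The concern.** The cutoff in section 6.1.6 makes the early-termination visit nearly redundant. Anyone terminated in, say, week 4 or week 8 has no planned outcome assessment, even if willing to come back at 3 months. A paired t-test needs both values, so these people leave the comparison by default, and the undertaking in section 9.2 cannot be met for the clinic measures.

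This matters because such losses may be related to the outcome. An adverse event, or a new diagnosis limiting exercise, is a plausible reason for termination and also a plausible reason for walking distance to fall. The study has one group and no comparator, so no second arm with similar losses can offset any selection. It would go directly into the pre-post change, which the pilot is meant to supply as a preliminary effect size.

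**Working it through.** **1. Timing.** Taking 3 months as 91 days, the ordinary window opens at 91 − 14 = day 77. Taking a month as about 30.4 days, 2.5 months is about day 76. The two limits differ by about one day, so section 6.1.6 adds about one day of eligibility to section 6.1.5. Termination at day 28 or day 56 leads to no planned assessment.

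**2. What is lost and what survives, for termination before about day 76.**
- No planned 3-month value: 6MWT, BMI, waist, blood pressure, lipids, Framingham score, PAVS. The 3-month step value is not assured either.
- Still available: daily Fitbit steps up to termination (section 6.1.1, Measures), which could enter the weekly-window comparison with week 2 that section 9.1 gives as an example; adverse events and the reason for leaving (section 5.7.2); completion data (section 9.2.2).

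**3. The plan's own attrition figure.** 47 / (1 − 0.20) = 58.75, rounded up to 59. This reproduces, and it leaves 59 − 47 = 12 planned losses from all causes.

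**4. Size of a possible bias.** The documents give neither a termination rate nor outcomes after termination, so this is an illustration. With q the share lost:

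overstatement = q × (mean change of those observed − mean change of those lost)

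Assume those observed gain 25 m, the clinically important difference in section 9.3, and that every person lost was lost before 2.5 months.

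| Lost of 59 | q | True change 0 m | −25 m | −50 m |
|---|---|---|---|---|
| 3 | 0.051 | 1.3 m | 2.5 m | 3.8 m |
| 6 | 0.102 | 2.5 m | 5.1 m | 7.6 m |
| 12 | 0.203 | 5.1 m | 10.2 m | 15.3 m |

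Example: (53 × 25 + 6 × (−50)) / 59 = 17.4 m over all enrolled, against 25 m observed, a difference of 7.6 m. The last row would require every planned loss to be a termination for worsening, which nothing in the documents suggests.

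**5. Scale.** Section 9.3 implies an SD of change of 25 / 0.33 = 75.8 m, or 28 / 0.41 = 68.3 m. The standard error of the mean change is 75.8 / √59 = 9.9 m or 68.3 / √47 = 10.0 m, so about 10 m either way.

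**6. Effect on a two-sided 5% paired t-test.** Suppose the true mean change over all 59 is zero, the SD is 68.3 m, and those lost declined by D = 25 or 50 m. With k lost, the observed mean is kD / (59 − k). For k = 6 and D = 50 it is 300 / 53 = 5.7 m. From the noncentral t distribution, the chance of p < 0.05 over this range of D is 5–6% with 3 lost, 6–9% with 6 lost and 10–24% with 12 lost.

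**The case against.** The strongest reply is that the text is conditional. Section 5.7.1 permits termination and does not require it, and the exclusion ground applies only where the criterion rules out further participation. No completer-only rule is written. Planned surgery, pregnancy, or a condition missed at screening is not in itself a worsened outcome, and the adverse-event ground is the more direct route for anyone harmed. Steps recorded before termination survive. In a pilot, a shift of 2.5 to 8 m is smaller than the sampling error. The remedy may also miss its main target, because a participant newly limited in exercise is the one most likely not to have the walk test.

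All of this stands, and it rules out a stronger reading. A reader might infer that the protocol systematically removes participants harmed by the intervention and that every efficacy endpoint is therefore inflated. The documents do not support that. They do not show who would be terminated or in what number. For blood pressure and BMI, where benefit is a fall, nothing indicates how terminated participants would have changed. Nor do such participants lack all outcome data, since their earlier steps remain.

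The reply does not remove the gap in collection. Once the investigator terminates someone before about 2.5 months, on either ground, no 3-month assessment is planned even if the person is willing, and no analysis rule says what then happens.

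**Conclusion.** The point holds as a limited defect in outcome collection. The 2.5-month condition nearly coincides with the opening of the ordinary window, so earlier terminations on either ground leave the paired analyses of the clinic measures and PAVS, contrary to section 9.2. A bias toward benefit is possible but not established. For 3 to 6 of 59 lost with true declines of 25 to 50 m, it would be about 2.5 to 8 m on the 6MWT, below one standard error of about 10 m. That range rests wholly on assumed losses and an assumed 25 m gain in the rest. The change is worth making because it is cheap and because a value never collected can later only be bounded, not recovered. The gap does not threaten the study as a whole.

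**What to change.** - **Sections 5.7.1 and 6.1.6:** state, for all investigator terminations, that ending the intervention does not end data collection unless the participant withdraws consent. Delete the 2.5-month condition, and seek the 3-month assessment at its scheduled date from every terminated participant who has not withdrawn consent.
- **Route:** extend to these participants the arrangements already in section 6.1.1 for remote follow-up (office-visit BMI and blood pressure, laboratory lipids from the record, self-measured waist), with the date of each value recorded.
- **Sections 9.1 and 9.2:** keep these participants in the analysis set. State how a missing 3-month value is handled, and add a sensitivity analysis that varies the assumed change in those still missing, as in the table above. This is needed in any case, because the 6MWT may still be omitted for some.

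The cost is protocol wording, a few extra contacts and some partial data. The final visits were already planned for the 59 enrolled. The rules on when physical activity is stopped do not change.
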